## 4 STUDY POPULATION

The study population will consist of children with peanut allergy. Study participation will require consent from a legally authorized representative. Subjects must meet all the inclusion criteria and none of the exclusion criteria.

All subjects will continue with their usual peanut-free diet and label reading of food products to avoid as much as possible any accidental peanut consumption for the duration of the study.

### 4.1 Inclusion Criteria

Subjects will be enrolled in this study only if they meet all of the following criteria:

1. Male or female children aged 4 through 11 years at Visit 1;
2. Physician-diagnosis of peanut allergy or children with a well-documented medical history of IgE-mediated symptoms after ingestion of peanut and currently following a strict peanut-free diet, but without a physician diagnosis;
3. Signed informed consent of parents/guardians of the child and child's assent (for children  $\geq 7$  years of age or as per the country-specific regulations);
4. Negative urine pregnancy test for female subjects of childbearing potential. Female subjects of childbearing potential must agree and commit to use effective medical methods of contraception for the entire duration of their participation in the study. Sexual abstinence will be accepted as an effective method of contraception;
5. Peanut-specific IgE level (ImmunoCAP system)  $>0.7$  kU/L;
6. Positive peanut SPT with a largest wheal diameter:
  - a.  $\geq 6$  mm for children 4 through 5 years of age at Visit 1,
  - b.  $\geq 8$  mm for children 6 years and above at Visit 1;
7. Positive DBPCFC at  $\leq 300$  mg peanut protein: the ED of peanut protein during the entry/screening DBPCFC is capped to 300 mg, as in subjects must have objective IgE-mediated symptoms to peanut leading to stopping the challenge at  $\leq 300$  mg peanut protein;
8. Ability to perform spirometry in accordance with the American Thoracic Society (ATS) guidelines 2007 (39) for subjects  $\geq 6$  years of age. Ability to perform peak expiratory flow (PEF) measurements for subjects  $\geq 5$  years of age. Subjects from 6 to 8 years of age who have documented inability to adequately perform spirometry can perform the PEF measurement instead. Subjects 4 years of age can be enrolled if they had no clinical features of moderate or severe persistent asthma within 1 year prior to visit 1.

---

 National Heart, Lung, and Blood Institute. Expert panel report 3: guidelines for the diagnosis and management of asthma - summary report, 2007. Available online at: <http://www.nhlbi.nih.gov/guidelines/asthma/asthsumm.pdf>. Accessed July 06, 2015.

9. Subject and/or parents/guardians willing to comply with all study requirements during the subject's participation in the study.

#### 4.2 Exclusion Criteria

Subjects will be enrolled in this study only if they meet none of the following criteria:

1. History of severe anaphylaxis to peanut with any of the following symptoms: hypotension, hypoxia, neurological compromise (collapse, loss of consciousness or incontinence);
2. Pregnancy or lactation;
3. Severe reaction during the entry/screening DBPCFC, defined as need for intubation, hypotension persisting after epinephrine administration, and/or the need for  $\geq 3$  doses of epinephrine;
4. Objective IgE-mediated symptoms to the placebo formula during the entry/screening DBPCFC and leading to stopping the challenge;
5. Viral upper respiratory infection or gastroenteritis within 7 days of a food challenge (challenge must be rescheduled to occur at least 7 days after recovery);
6. Any clinically significant abnormality identified at the time of screening such as major infectious diseases (for example chicken pox, measles) which in the judgment of the Investigator may preclude safe participation or strict compliance with the protocol procedures (subjects can be considered for the study after recovery from these diseases);
7. Generalized dermatologic disease (for example active atopic dermatitis, uncontrolled generalized active eczema, ichthyosis vulgaris) extending widely on the skin and especially on the back with no intact zones to apply the Viaskin® patches;
8. Symptomatic seasonal allergies that may interfere with the conduct of a DBPCFC. Subjects should be screened at a time when such allergies are asymptomatic (for example outside of the culprit season);
9. Known hypersensitivity to any of the Viaskin® patch components (except peanut), including the adhesive film;
10. Known hypersensitivity to any component of the food challenge formula (except peanut);
11. Inability to discontinue short-acting antihistamines or long-acting antihistamines for the minimum wash-out periods as specified in the table in [APPENDIX 4](#)) prior to the skin prick testings or the food challenges;
12. Spirometry forced expiratory volume in 1 second ( $FEV_1$ )  $< 80\%$  of the predicted value at screening (visit 1) for subjects  $\geq 6$  years of age and able to perform the spirometry, or PEF  $< 80\%$  of predicted value at screening (visit 1) for subjects performing only the PEF measurements.
13. Diagnosis of asthma that fulfills any of the following criteria:

- a. Uncontrolled persistent asthma as defined by National Asthma Education and Prevention Program Asthma guidelines 2007 (40) or by Global Initiative for Asthma guidelines 2015 (41),
  - b. Asthma treated with either a high daily dose of inhaled corticosteroid or with a combination therapy of a medium daily dose of inhaled corticosteroid with a long-acting inhaled  $\beta$ 2-agonist or with a combination therapy of a high daily dose of inhaled corticosteroid with a long-acting inhaled  $\beta$ 2-agonist (a list of daily dosages of inhaled corticosteroid is provided in [APPENDIX 2](#)). Asthmatic subjects treated with a medium daily dose of inhaled corticosteroids are eligible. Intermittent asthmatic subjects who require intermittent use of inhaled corticosteroids for rescue are also eligible,
  - c. Two or more systemic corticosteroid courses for asthma in the past year or 1 oral corticosteroid course for asthma within 3 months prior to Visit 1, or during screening period (unless used to treat symptoms triggered by the DBPCFC),
  - d. Prior intubation/mechanical ventilation for asthma within 1 year prior to Visit 1, or during screening;
14. Receiving  $\beta$ -blocking agents, angiotensin-converting enzyme inhibitors, angiotensin-receptor blockers, calcium channel blockers or tricyclic antidepressant therapy;
  15. Received anti-tumor necrosis factor drugs or anti-IgE drugs (such as omalizumab) or any biologic immunomodulatory therapy within 1 year prior to Visit 1, during screening period or during study participation;
  16. Use of systemic long-acting corticosteroids within 12 weeks prior to Visit 1 and/or use of systemic short-acting corticosteroids within 4 weeks prior to Visit 1 or during screening (unless used for DBPCFC symptoms) (see [APPENDIX 3](#));
  17. Prior or concomitant history of any immunotherapy to any food allergy (for example EPIT, OIT, SLIT, or specific oral tolerance induction);
  18. Receiving or planning to receive any aeroallergen immunotherapy during their participation in the study. Aeroallergen immunotherapy must be discontinued at the time of Visit 1;
  19. Subject or parents/guardians of subjects with obvious excessive anxiety and unlikely to cope with the conditions of a food challenge;
  20. Past or currently active disease(s) which, in the opinion of the Investigator or the Sponsor, may affect the subject's participation in this study or place the subject at increased risk during participation in the study, including but not limited to eosinophilic gastrointestinal disorders, autoimmune disorders, immunodeficiency, malignancy, uncontrolled diseases (for example hypertension, psychiatric illness, cardiac disease), or other disorders (for example liver, gastrointestinal, kidney, cardiovascular, pulmonary disease, or blood disorders);
  21. Any disorder in which epinephrine is contraindicated such as coronary artery disease, uncontrolled hypertension, or serious ventricular arrhythmias;

22. Subjects unable to follow the protocol requirements;
23. Current participation in another clinical trial or participation in another clinical trial in the last 3 months prior to visit 1;
24. Diagnosis of mast cell disorders including mastocytosis or urticaria pigmentosa as well as hereditary or idiopathic angioedema;
25. Subjects receiving cyclosporine or other immunosuppressive agents within 1 year prior to Visit 1, or during the screening period or during study participation. Topical calcineurin inhibitors are permitted;
26. Subjects with severe psychiatric, psychological or neurological disorders;
27. Subjects being in any relationship or dependency with the sponsor and/or the investigator or the study staff.

### 4.3 Patient Withdrawal and Replacement

#### 4.3.1 *Criteria for Withdrawal from Study Treatment and Study*

Subjects may withdraw from the study including follow-up at any time without penalty and for any reason without prejudice to their future medical care.

Subjects must be withdrawn from the **study treatment** under the following circumstances:

- Pregnancy (see [Section 6.2.1.7](#));
- Severe “maculo-papular rash” or severe “dermatitis” failed to be controlled by adequate corrective treatments (including topical corticosteroids) and in spite of several study treatment interruptions;
- Severe anaphylaxis (or stage 3 anaphylaxis) (see [APPENDIX 5](#)) related to Viaskin® Peanut 250 µg patch application;
- More than 1 epinephrine injection for an AE related to Viaskin® Peanut 250 µg patch application (and not occurring during the DBPCFC).

If subjects are to withdraw due to pregnancy, the procedures that should be followed are described in [Section 6.2.1.7](#).

Subjects may be required to withdraw from the **study treatment or study** after discussion with the Sponsor and/or Investigator for the following reasons:

- AE(s);
- At the discretion of the Investigator, if she/he decides that it is in the subject’s best interest to be withdrawn from the study;
- The subject is unwilling to continue in the study (consent withdrawal);
- Lack of compliance with protocol requirements and procedures;
- The Sponsor, Regulatory Authorities, or Independent Ethics Committees (IECs)/Institutional Review Boards (IRBs) for any reason, stop the study;

- The subject fails to return to the clinic for scheduled visits and does not respond to telephone or written attempts at contact (lost to follow-up);
- Premature termination of the entire study as described in [Section 9.11](#).

In all cases, the primary reason for withdrawal, must be recorded in the e-CRF.

#### **4.3.2 Study Stopping Rules**

Study enrollment will be suspended pending an expedited safety review by the independent DSMB if any of the following occur:

1. Any death related to Viaskin® patch dosing;
2. More than one case of severe anaphylaxis (or stage 3 anaphylaxis) (see [APPENDIX 5](#)) related to Viaskin® Peanut 250 µg patch application (not occurring during the DBPCFC);
3. More than 3 subjects requiring more than 1 injection of epinephrine for an AE related to the Viaskin® Peanut 250 µg patch application (and not occurring during the DBPCFC).

Upon safety review, 1 of the following outcomes will be determined:

- Accrual to the study may continue without modification;
- Accrual to the study may continue with modifications as prescribed by the DSMB;
- Accrual to the study should be discontinued.

#### **4.3.3 Replacement of Withdrawn Subjects**

Subjects who withdraw prematurely after having been randomized and having received at least 1 dose of the study drug will not be replaced.

#### **4.3.4 Data Collection and Follow-up after Withdrawal**

If a subject is prematurely withdrawn from the study drug for any reason before completing all study visits, the Investigator must make every effort to perform the evaluations described for the Early Termination Visit (see [Section 7.2.12](#)). The Investigator must furthermore complete all appropriate subject diary and e-CRF pages, providing the date and explanation for the subject's withdrawal/discontinuation. When indicated, the Investigator must arrange for appropriate follow-up and/or alternative medical care of the discontinued subject.

If the subject fails to attend a scheduled End of Study Visit, there will be at least 2 attempts to contact the subject's parents/guardians via telephone and written communication. If these receive no reply, the subject will be considered as lost to follow-up.

### **4.4 Planned Sample Size and Number of Study Centers**

It is planned to randomize 330 subjects at 28 to 40 centers in 4 to 7 countries for this study. See [Section 8.10](#) for a discussion of sample size.

## 4.5 Patient Identification and Randomization

### 4.5.1 Patient Identification

At screening, each subject will receive a unique, 4-digit, screening number. Screened subjects who drop out of the study before randomization will retain their screening number. The screening number for each subject will be a combination of the 2-digit site number plus the 2-digit number assigned to the subject according to her/his chronological order of screening at that site. The screening number will be used as the subject identifier throughout the study.

### 4.5.2 Randomization Scheme

An IWRS will randomize subjects and assign the appropriate treatment number or kit number. Subjects will be randomized on a 2:1 basis to Viaskin® Peanut 250 µg or placebo.

Randomization will be stratified by center and by screening ED and managed centrally. The randomization scheme will ensure that the ratio of active treatment to placebo is maintained in Stratum 1 (children with a screening ED from 1 mg to 10 mg) and Stratum 2 (children with a screening ED from 30 mg to 300 mg).

No randomization ratio will be fixed for the 2 screening ED strata; however, according to the Phase IIb VIPES study, the following distribution could be expected:

- 1/3 of children with a screening ED from 1 mg to 10 mg;
- 2/3 of children with a screening ED from 30 mg to 300 mg.

The randomization codes will be maintained by IWRS.

Blinding and breaking the blind procedures are described in [Section 5.4](#).

### 4.5.3 Allocation/Randomization of Patients to Treatment

Randomization of subjects to treatment will occur at Visit 4 after all screening procedures have been performed and eligibility for the study confirmed. Each randomized subject will be assigned by the IWRS a kit number based on a pre-defined algorithm/pre-defined randomization list.

## 5 STUDY DRUG

### 5.1 Identity

The study drug, Viaskin® Peanut, is a cutaneous patch (Viaskin® patch) containing a dry deposit of a formulation of peanut protein extract. The Viaskin patch is a 34 mm-side long square-shaped patch with a rounded condensation chamber of 18 mm-inner diameter. The peanut allergens are deposited on the backing of the patch chamber by electrospraying a liquid peanut protein formulation, which dries instantly. The outer adhesive part of the condensation chamber is composed of a small band of adhesive foam to stick to the skin. The Viaskin® patch is identical to the ones used in prior clinical studies, but now also includes a hypoallergenic adhesive film that will help prevent the Viaskin® patch from coming off inadvertently.

The drug substance is an unmodified, lyophilized peanut extract produced from the extraction and freeze drying of defatted peanut flour. The drug substance contains the biologically active ingredients, the peanut proteins. This drug substance derives from a natural source material of biologic origin, the peanut seed from the Virginia variety of *Arachis hypogaea* and the extract contains all peanut proteins.

The other components of the study drug are inactive excipients: ethanol, surfactant (Polyoxyl 20 oleyl ether), and buffering agents (trometamol and histidine).

Study subjects will be administered either Viaskin® Peanut at 250 µg peanut protein (active) or Viaskin® patch with placebo, according to randomization. The placebo treatment will consist of a similar formulation, but will be devoid of peanut protein.

[figure not shown]
Both, Viaskin® Peanut 250 µg and Viaskin® placebo will be manufactured by CCI [REDACTED] and labeled, packaged and released for clinical use by CCI [REDACTED], in accordance with the requirements of Good Manufacturing Practices.

### 5.2 Administration

Subjects will be randomized to receive either active Viaskin® Peanut 250 µg or placebo, in a 2:1 ratio (active versus placebo).

During the 12-month blinded treatment period, except for the first 2 weeks (see below), the Viaskin® patch will be applied on the skin for 24 hours ( $\pm$  4 hours of allowance) every day and renewed on a daily basis, 1 new patch per day.

The location of patch application is the inter-scapular area of the back of the subjects. There will be 6 zones for applying the patch, 3 on each side of the spine (see Figure 2). The first Viaskin® patch will be applied on zone 1, the second on zone 2 (after removal of the first patch), and so forth, until all 6 zones have been used. After zone 6, dosing restarts with zone 1 and continues sequentially, as described.

**Figure 2: Schematic Representation of Viaskin® Patch Application on the Back of the Subjects**

To better ensure the safety of the Viaskin® patch at the initiation of treatment, the duration of application of the Viaskin® patch will be progressively increased as follows:

- During the first week (from Day 1 through Day 7), the patches will be applied for 6 hours every day;
- During the second week (from Day 8 through Day 14), the patches will be applied for 12 hours every day;
- From the third week onwards (Day 15), the patches will be applied for the entire 24 hours.

If possible, the subjects should take advantage of their shower/bath time to change the patch. The previous Viaskin® patch should be removed just before the shower/bath, and the new Viaskin® patch should be applied a few minutes after the shower/bath and after drying the skin. Application of the Viaskin® patch at a similar time for each daily application (morning or evening) is recommended. If the subject does not bathe or shower daily or at the same time daily, it is recommended that the zone to which the patch will be applied be cleaned with a moist disposable napkin or tissue and dried prior to application.

A Viaskin® patch must not be re-applied. In case the Viaskin® patch comes off, it should be immediately discarded.

A new patch can be applied the same day to replace the previous patch that came off only if that patch came off within 2 hours after being applied. However, no new patch should be applied the same day if the previous patch came off more than 2 hours after being applied. In that case, a new patch will be applied once 24 hours have passed since the previous patch (the one that came off) was applied. After the Viaskin® patch comes off,

or after removing a Viaskin® patch to apply a new one, it is recommended that the subject's parents/guardians wipes the zone with a moist disposable napkin or a moist disposable tissue and then washes her/his hands to prevent accidental manual transmission of peanut protein.

After the first application of the Viaskin® patch at the study site, all subjects will be observed for 3 hours before being discharged in order to check and grade any reactions under or around the patch.

Because the study includes children aged 4 through 5 years, additional safety measures have been adopted and generalized to all ages. On Day 4 and on Day 22, specific phone contacts will be made to the parents/guardians to assess the safety of patch applications on the back. If required, the subjects may come to the site sooner than planned to be seen and evaluated by the Investigator.

Of note, the recommended duration of daily Viaskin® patch application is 24 hours of application per day. However, any daily duration of Viaskin® patch application of 24 hours  $\pm$  4 hours will be allowed.

### ***5.2.1 Adjustment of Viaskin® Patch Application in Case of Local or Systemic Reactions***

When subjects are unable to apply the Viaskin® patch for the recommended durations as described above because of local intense or severe reactions, under or adjacent to the patch site, the patch should be removed immediately, the site of application wiped with a moist disposable tissue and a topical corticosteroid medication might be topically applied to treat the reaction. The parents/guardians should take a photo of the back of the subject to document how intense and extended the local reactions are. In the specific case of local intense or severe reactions, it is mandatory that the next Viaskin® patch is applied only the next day on the next zone; no other Viaskin® patch must be applied the same day. In case of re-appearance of the local intense or severe reactions after application of the next patch the following day, the patch must again be removed. The next Viaskin® patch should be applied only the next day on the next zone. And the same process is repeated every day after patch application in case of local intense or severe reactions.

As a consequence, the daily duration of Viaskin® patch application should be adjusted/reduced as necessary, and subjects may need more than the 14 days previously described before they can apply and tolerate the Viaskin® patch for the full 24 hours daily.

In case of any suspected systemic reactions related to patch application (including cutaneous reactions distant from the sites of patch application), the same safety precautions should be followed: the Viaskin® patch is removed immediately, the site of application wiped with a moist disposable tissue and a treatment can be given to treat the reaction: antihistamines or topical corticosteroids with additional oral corticosteroids or similar anti-allergic drugs, as deemed necessary by the Investigator. The next Viaskin® patch should be applied the next day on the next zone. As a consequence, the daily duration of patch application should be adjusted/reduced as necessary, and subjects may need more time than initially defined before they can apply the Viaskin® patch for the full 24 hours daily.

The subject's parents/guardians will be instructed to contact the Investigator in case of intense or severe local reactions lasting for more than 1 day or any unexpected reactions during the treatment period, in particular in case of appearance of vesicles under the Viaskin® patch or close to the Viaskin® patch site application. It is then recommended that the parents/guardian take a photo of the back of the subject to document these intense or severe reactions.

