- Change from Baseline will be summarized using shift tables where appropriate.

The following conventions will be considered regarding study assessments and time points:

- Date and time of the first patch application will be reported in the eCRF. The baseline value is the last measurement before date and time of first patch application, in other words, Visit 4 data are taken into account for the Baseline, unless the date/time clearly indicates that the value is after the patch application. For physical exam, even if the time is not reported, V4 will be taken into account as Baseline.
- The ‘end of study’ assessment is defined as the last available post-treatment assessment.
- “Treatment Day” will be calculated relative to date of first patch application (Treatment day 1 = Date of first patch).
- Assessments collected at unscheduled visits will not be included in summary tables but only listed.
- Assessments outside of protocol allowable windows will be taken into account in the analysis according to the visit in which the data are entered.
- Early termination assessments will be analyzed as having occurred at the next scheduled assessment.

The following conventions will be considered regarding confidence p-values and confidence intervals (CI):

- P-values greater than or equal to 0.001, in general, will be presented to three decimal places. P-values less than 0.001 will be presented as “<0.001”.
- Confidence intervals will be presented to one more decimal place than the raw data.

The following conventions will be applied on diary data dates, for each incomplete patch application or removal date:

- Incomplete application date:
  - ⌘ During the first 14 days of patch application: imputed as removal dates (if removal date is complete).
  - ⌘ Beyond the first 14 days: imputed as removal date -1 (if removal date is complete).

- Incomplete removal date:
  - ⌘ During the first 14 days of patch application: imputed as application date (if application date is complete).
  - ⌘ Beyond the first 14 days: imputed as application date +1 (if application date is complete).

No imputations will be performed on time of application/removal unless explicitly described for specific analyses.

Titles for tables and listings produced will specify the type of data reported as well as the population concerned (in parentheses).

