- r D1 to D7,
- r D8 to D14,
- r D15 to M3 (D90),
- r M3 (D91) to M6 (D185),
- r M6 (D186) to M9 (D275),
- r M9 (D276) to M12 (end of treatment),
- r D15 to M12

If more than one patch is applied the same day, the daily duration considered is the cumulative application duration of these patches.

In case patches are sequentially applied on the same day: if the end date/time of first patch is not documented, the application date/time of the next patch will be used for imputation.

The percentage of days with no patch application, per subject diary reported data, will also be tabulated, overall and for each of the above periods.

A patch will be considered as “applied” if the date and time of application is documented in the diary.

The start and/or end date/time of patch application used to calculate the duration of patch application are extracted from the diary.

Inconsistencies in the diaries are not queried and only self-evident corrections according to the Data Validation specifications will be made; therefore, inconsistent date/time of patch application or patch removal may remain in the data. In case where calculation of patch application duration leads to a negative value or duration cannot be calculated (missing date or time of removal or invalid dates or times) then:

CCI

CONFIDENTIAL

Project Document Version No. 3.0

Project Document Effective Date: 04-Oct-2017

Page 31 of 79

- The duration of patch application will be considered as ‘unknown’ and not used in the calculation of the average duration of patch application
- For any other calculation based on the number of days with patch application, this day will be considered as a day with application.

These data will be reported as:

- Descriptive statistics for study duration, treatment exposure duration, total dose of protein and compliance (overall and by visit - except for study duration -),
- Number and percent per category of overall exposure (in days, categories are: 1-7, 8-14, 15-30, 31-90, 91-185, 186-275, 276-365, >365), compliance in classes (<80%, ≥80%).

Study duration, treatment exposure and compliance will be summarized for the Safety population in tables that will be produced for each treatment group and overall (except for peanut protein dose that will only be described for the Viaskin Peanut 250 µg arm), globally and by screening ED subgroup.

All data including documentation of treatment interruptions will be listed by treatment group.

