#### 4.9.3 Local skin reactions as collected in the diary

Number and percentage of subjects with evaluable diary data will be presented.

Local skin reactions at sites of Viaskin® application as assessed by the patient and documented in the diary during the first 6 months of the study treatment will be summarized for itching, redness, swelling, and any local reaction (itching, redness and swelling) using:

- The number and percentage of subjects by maximum severity grade reported (1, 2 or 3) among subjects with evaluable diary data and among subjects with a reaction (grade  $\geq 1$ )
- The number and proportion of days with a reaction reported (based on days with patches graded by type of reaction or for at least one reaction between itching, redness and swelling when reported on any local reaction) among subjects diary data,
- The proportion of days scored by severity grade (worst severity grade per day is considered).

All proportions will be calculated as

$$\left( \frac{\text{Number of days with a reaction reported}}{\text{Number of days with patches graded}} \right)$$

Proportion of days with no assessment of local skin reaction out the number of patches entered in the diary will be provided.

The number of days with a reaction reported and number of days with patches graded will be calculated based on removal dates.

The periods considered for the reporting will be:

- r The overall first 6 months (D1 to D180),
- r Month 1 (D1 to D30),
- r Month 2 (D31 to D60),
- r Month 3 (D61 to D90),
- r Month 4 (D91 to D120),
- r Month 5 (D121 to D150),
- r Month 6 (D151 to D180)

The above analysis will be repeated for subjects with filaggrin gene mutations versus wild type subjects.

All local skin reactions reported by the subject will be listed.

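### The SAP's calendar-only date rule adds 24 h of wear to same-day early removals after Day 14 when the date is incomplete, and in the first 14 days it discards patches that cross midnight

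*Protocol*

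**What the plan says.** **The date rule (SAP 4.2, General Considerations).** For an incomplete removal date in the initial period: "During the first 14 days of patch application: imputed as application date (if application date is complete". Later: "Beyond the first 14 days: imputed as application date +1 (if application date is complete". The mirror rule for an incomplete application date after that period is "Beyond the first 14 days: imputed as removal date -1 (if removal date is complete". Clock times are left as recorded: "No imputations will be performed on time of application/removal unless explicitly described for specific analyses".

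**The screen (SAP 4.7).** "In case where calculation of patch application duration leads to a negative value or duration cannot be calculated", the duration is classed as unknown and left out of the average, although the day still counts as one with a patch. The section sets no upper limit on a patch's duration; its 100% cap applies to compliance.

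**The protocol background.** Section 5.2 plans 6 h of wear in week 1, 12 h in week 2 and 24 h (±4 h) from Day 15. Application "at a similar time for each daily application (morning or evening) is recommended". Section 5.2.1 calls for immediate removal after an intense or severe local reaction, repeated on later days if needed, and notes that "subjects may need more than the 14 days previously described before they can apply and tolerate" the patch for a whole day. Section 6.2.7 has families record each application and removal time, and the reason for any early removal.

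**Where the dates are used.** They feed the descriptive average daily application duration (SAP 4.7). They also feed the diary skin-reaction tables for D1–D180 (SAP 4.9.3): "The number of days with a reaction reported and number of days with patches graded will be calculated based on removal dates".

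**The concern.** The rule looks only at the study day. After Day 14 it assumes that every patch with an incomplete date was worn overnight, although the protocol itself expects some to come off within hours. The recorded time is then attached to the wrong date. The result is a positive number, so nothing flags it.

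The children exposed to this error are those who react. In the Phase IIb study (Protocol 1.1.1.2.3), local reactions occurred in more than 90% of subjects on any active dose and 50% on placebo, so affected patches would be expected mainly in the active arm. There the error would hide reduced wear, which is what the wear-time summary is meant to show.

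In the first 14 days the assumption fails the other way. A 12 h patch applied after noon, or a 6 h patch applied after 18:00, comes off on the next date. The same-day rule makes its duration negative, and a usable record is lost.

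**Working it through.** The plan states no wear-time figure to reproduce. The check applies its rules to worked cases.

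**Step 1. One patch, both clock times recorded, removal date incomplete.** Imputed wear = (imputed removal date + recorded time) − (application date + recorded time).

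| Period | On | Truly off | True wear | Rule gives | Error |
|---|---|---|---|---|---|
| After Day 14 | 08:00 | 11:00 same day | 3 h | 27 h | +24 h |
| After Day 14 | 08:00 | 14:00 same day | 6 h | 30 h | +24 h |
| After Day 14 | 08:00 | 20:00 same day | 12 h | 36 h | +24 h |
| After Day 14 | 20:00 | 23:00 same day | 3 h | 27 h | +24 h |
| After Day 14 | 20:00 | 02:00 next day | 6 h | 6 h | 0 |
| After Day 14 | 08:00 | 08:00 next day | 24 h | 24 h | 0 |
| After Day 14 | 20:00 | 00:00 two dates on | 28 h | 4 h | −24 h |
| First 14 days | 08:00 | 14:00 or 20:00 same day | 6 or 12 h | 6 or 12 h | 0 |
| First 14 days | 20:00 | 02:00 next day | 6 h | −18 h | unknown |
| First 14 days | 20:00 | 08:00 next day | 12 h | −12 h | unknown |

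The mirror rule behaves alike. A patch on at 08:00 and off at 11:00 on Day 40, with the application date incomplete, is dated as applied on Day 39, giving 27 h.

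**Step 2. Effect on a child's period mean.** With k affected patches and n days, all with usable durations, inflation = 24k/n.

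- D15–D90: n = 90 − 15 + 1 = 76. For k = 1, 5, 10: +0.32, +1.58, +3.16 h.
- D15–D365 (taking Month 12 as Day 365): n = 351. For k = 1, 5, 10: +0.07, +0.34, +0.68 h.

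The values of k are assumptions.

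**Step 3. Would classing these durations as unknown be enough?** Illustration over D15–D90: k patches truly worn 6 h, all with incomplete dates, and the rest worn 24 h.

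- True mean = [24(76 − k) + 6k]/76. For k = 1, 5, 10: 23.76, 22.82, 21.63 h.
- SAP rule = [24(76 − k) + 30k]/76: 24.08, 24.39, 24.79 h.
- Short patches dropped as unknown: 24.00 h each time.

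Dropping them removes part of the error, but the mean stays too high.

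**Step 4. Diary reaction days.** Two patterns, with patches applied at 08:00:

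- *Isolated early removal.* The Day 39 patch comes off at 08:00 on Day 40. The Day 40 patch comes off at 11:00 the same day, date incomplete. The Day 41 patch comes off on Day 42. True removal dates are 40, 40, 42; imputed dates are 40, 41, 42. The rule adds a distinct day.
- *Consecutive early removals.* The Day 40 patch comes off on Day 40, date incomplete, and is dated Day 41. The Day 41 patch comes off on Day 41. Two true days become one.

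The direction depends on the pattern, and the dates enter both numerator and denominator of the proportions.

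**The case against.** The strongest case on the other side is that the error needs several things together and reaches nothing that matters for inference. The date must be incomplete while the time is recorded; if the time is missing too, SAP 4.7 excludes the duration. Investigators check the diary at each visit (Protocol 6.2.7). SAP 4.7 permits self-evident corrections under data validation specifications that are not in these documents. When a second patch goes on the same day and the first has no documented end, its application time closes the first. The outputs are descriptive.

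Most of this stands, and it limits the point. It does not remove it. SAP 4.7 says diary inconsistencies are not queried, and no written rule stops a 27 h or 36 h value. The same-day replacement rule does not help after an intense or severe local reaction, because Protocol 5.2.1 then bars another patch that day; after a suspected systemic reaction it puts the next patch on the next day.

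Four stronger readings are tempting, and the documents do not support them:

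- *Evening application inflates wear.* In the first 14 days, patches that cross midnight become unknown and are not overstated. After Day 14, an evening patch removed early after midnight is dated correctly; only removal before midnight gains 24 h.
- *Reaction days are undercounted.* Step 4 shows that the count can move either way.
- *The inflation is a large percentage.* That needs a child who removes nearly every patch within hours and an assumed rate of incomplete dates. No such rate is given.
- *Efficacy or the per-protocol set is affected.* The primary endpoint comes from the food challenge. Compliance, with its 80% threshold, uses patches dispensed minus returned over exposure days. Total dose uses exposure days. None of these uses wear hours or removal dates.

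**Conclusion.** The point holds as a narrow defect in a stated rule. After Day 14, a same-day early removal with a recorded time and an incomplete date gains exactly 24 h, from either the removal-date rule or its mirror, and SAP 4.7 does not detect it. In the first 14 days the fault is needless loss of data. Per affected patch, a child's mean rises by about 0.32 h over D15–D90 and 0.07 h over D15–D365, assuming every day has a usable duration. The total effect cannot be sized because the frequency of incomplete dates is not given. That it falls mainly on the active arm is an expectation from the earlier trial's reaction rates; these documents cannot confirm it for incomplete dates. The consequence is confined to descriptive exposure and diary tables. It is a minor correction, worth making because the diary already collects what is needed.

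**What to change.** Amend SAP 4.2 so that, when both clock times are recorded, they help to decide the date:

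- *First 14 days:* same date if the removal time is later than the application time, otherwise the next date.
- *After Day 14, no early removal recorded:* keep the one-day offset.
- *After Day 14, early removal recorded:* same date if the removal time is later than the application time, otherwise the next date. For wear under 24 h the two times settle the date uniquely.
- *Incomplete application dates:* apply the mirror of these rules.
- *Unknown:* use only when the date still cannot be determined.

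Report the number of imputed and unknown durations by arm, since Step 3 shows that dropping short-wear patches also biases the mean upward.

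Two limits remain. A late-evening patch worn to the top of the 24 ± 4 h allowance can still lose 24 h (last after-Day-14 row of the table). Restoring true dates can also leave two patches sharing a removal date in the diary tables; that follows from the counting basis in SAP 4.9.3.

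The cost is a few lines of SAP text and programming, with no new data collection.
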